Our primary focus in this study is the short and long term behavioral impact of e-cigarettes. We considered a trial that was powered on e-cigarette uptake or substitution of conventional cigarettes (Specific Aim 1). These questions alone are important outcomes that would inform the public health debate. However, it would be a missed opportunity to not ask about overall exposure (Specific Aim 2) and quitting (Specific Aim 3). We also believe that, if group differences in quitting do exist, it would be entirely shortsighted if we lacked sensitivity (i.e., power) to demonstrate them. So while we focus on uptake, adoption, and patterns of dual use, we power our study on the most stringent outcome: point prevalence abstinence at 6 months (continuous abstinence is more stringent, but inappropriate here since there is no quit date to commence cessation). Table 4 depicts various sample size scenarios, under the guiding belief that e-cigarettes will facilitate quitting (see Intro). These scenarios are all based on proposed 2:1 randomization, in an effort to have better precision (i.e., tighter confidence intervals) for our primary outcome, involving only the e-cigarette group. Our base rates for quitting come from our three prior/ongoing nationwide studies, in which 6-month abstinence rates within control group ranged 4-13% (75, 76). We also recognize other population estimates (~5%) of population-based quitting (133), and ultimately take an estimate within this range: 8%. As for quit rates in the e-cigarette group, we note outcomes from most relevant study yet published: an uncontrolled observational cohort (i.e., naturalistic) study of smokers given e-cigarettes for up to 6 months (47), in which 23% (ITT, based on full N) and 33-39% (respondent only analyses) were quit at 6 months. We think that is a bit high. Given that we provide e-cigarettes for only ~1month, we expect somewhat lower rates of quitting. We power on a RR of 2.0: 8% vs. 16%. We would like to detect even smaller increases in quit rates (5% vs. 10%; RR still 2.0), but clearly that is not feasible. We thus decide on 600 participants, but inflate this by 10% to account for attrition: 660 participants to be enrolled

Table 4: Sample Size Needs

		Quit Rate in E-Cigarette Group				
		10%	15%	16%	20%	25%
Quit Rate in Control Group	5%	1015	332	287	179	117
	8%	7324	755	600	305	174
	10%		1576	1135	463	233
	15%				2067	2486

2:1 randomization (e cig:control); 80% power

(440 e-cigarette vs. 220 control). With this sample, we have 80% power to detect differences of 10% vs. 18.5%, with a two-sided $\alpha=0.05$ chi-square test. If provision of e-cigarettes should undermine quitting, we are able to detect a decrement of 4% (8% vs. 4%; OR = .48; 95% CI: 0.23 - 0.98).

Precision of Proportional estimates within Aim 1 With 440 e-cigarette participants, a two-sided 95.0% confidence interval will have a maximum half-width of 0.047 (for any outcome in Aim1) (e.g., 95% CI on an observed rate of 50% would range from 0.453 to 0.547). As the observed proportion deviates from 50% (either higher or lower), the 95% confidence interval will decrease in width, providing more precision on the estimate (e.g., 95% CI on 90% would range from 0.872 to 0.928). A confidence interval as wide as +/- 5% is a relatively small width and one we are willing to accept for our estimates on uptake, adoption, and patterns of dual use.

Sample size estimate for local subset, to capture biomarkers of exposure We searched for prospective e-cigarette studies (controlled or not) that were NOT cessation based but reported on biomarkers, either CO or cotinine. We found only one (47) but acute decreases (within 1 month) in CO were only indirectly reported (in graph, separated by smoking group outcomes). Consistent with those data, we expect an overall decrease in CO within 1month of 35%, compared with no such decreases within the control group. A sample size of 80 in the e-cigarette local subset group (total of n=120 for the local subset who complete the baseline in-person lab visit) will have at least 80% power to detect a 35% decrease in CO (23.5ppm to 15.3ppm in the e-cigarette group vs. no change in the control group, assuming a standard deviation of 15.0 in the control group and 10.0 in the e-cigarette group (standard deviations were estimated from the interquartile ranges reported in the Polosa study (47) using standard procedures (134)). We expect no group differences in cotinine. We recognize that this technically implies a test of equivalence, and we are willing to accept up to +/-3% difference to conclude equivalence. With a local subset sample size of n=120 (40 control and 80 e-cigarette), $\alpha=0.05$, a two-sided t-test has >90% power to reject the null hypothesis that the two groups are not equivalent (1400ng/ml +/- 45ng/ml) in favor of the alternative hypothesis that the mean cotinine levels of the two groups are equivalent (assuming an expected difference in means of 0ng/ml and a common standard deviation of 70.0ng/ml) (135).

Statistical Considerations – Data Analyses

All analyses are based on an intent-to-treat approach, and are nearly identical to analyses from our prior studies. Exploratory analysis will be performed on all outcomes, and both graphical displays and summary statistics will help determine if transformations will be needed. Any significant baseline differences between groups will be included in regression analyses described below. Missing Data: The most conservative approach for handling missing data (136) is to substitute them with baseline values, assuming outcomes have all returned to baseline, with no quit attempts made. If this assumption is incorrect, it biases the results towards the null by reducing between group differences (136). SRNT recommendations (136) suggest that when there are small amounts of missing data (< 10%) the conservative approach can be used with little bias in outcome. If missing data >10%, we will calculate results not only using this conservative method but also using methods in which missing data are imputed as described in the SRNT guidelines. We will also assess whether dropout is differential by study group. In our current and recent studies of cessation induction, this has not been the case, and we expect similar results here. Finally, though sex/gender is not an explicit focus, we are well poised, given our sample size, to address **potential sex/gender influences** on study outcomes.

Hyp 1a: Within the e-cigarette group, we hypothesize that at least 90% of smokers will try at least once, 45% will use regularly (at least 4/7 days, at any time during follow-up), 25% will use daily for ≥ 7 days (at any time during follow-up), 25%/10% will be using at least some/daily at final follow-up, and 20% will independently purchase e-cigarettes. Within the e-cigarette group (N=440), we will analyze prevalence of each definition of uptake. We will estimate each of these parameters, and the 95% confidence interval for each proportion.

Hyp1b: Among smokers in the e-cigarette group, 40% will show a minimum of 50% reduction in cigarettes per day, and as a group, e-cigarette users will show greater decreases in cigs/day as compared to control. Reduction of cigarettes per day will be calculated based on the TLFB at baseline and 6 months for both groups, with “reducers” defined as those that reduce cigarettes per day by $\geq 50\%$. We will estimate the mean reduction, 95% confidence interval on the reduction, and the proportion of those that are considered “reducers” in both groups, the latter tested via a chi-square test with $\alpha=0.05$ two-sided significance level.

Hyp2: Within a subset of locally recruited smokers, we hypothesize that use of e-cigarettes will lead to significant decreases in CO and NNAL, but no net change in overall nicotine exposure. Changes in CO, NNAL and cotinine will be calculated based on the baseline, 1, and 6-month measurements. Mean change in CO/NNAL (thru 1 and 6 months) will be compared via a two-sample t-test with $\alpha=0.05$ significant level. In order to test equivalence for change in cotinine between the two groups, the TOST procedure (137) will be followed where two one-sided tests will be used to test that the difference in the change between groups (Δ) is within the +/-3% bounds that we are willing to accept ($H_{01}: \Delta < -3\%$; $H_{02}: \Delta < +3\%$). If Δ is contained completely within the +/-3% bounds, then equivalence will be concluded. We will use an $\alpha=0.05$ significance level.

Hyp 3: Provision and use of e-cigarettes will lead to increased incidence of (Hyp3a) quit attempts, (Hyp 3b) cessation, and (Hyp 3c) motivation/confidence to quit. Logistic regression analyses will be performed with (1) any quit attempt [QA] within 6 months (1=one or more quit attempts, 0=none), (2) any 24hr QA (same), (3) point prevalence abstinence at 6 months (1=7 day abstinence at 6 months, 0=not abstinent), and (4) floating abstinence (1=any 7 day period of abstinence during study, 0=no abstinence) as the outcomes and group (e-cigarette vs. control) as the covariate. The coefficient on group provides a log odds ratio for measuring the odds of (1) any self-defined QA's, (2) 24hr QA's, (3) point prevalence abstinence, and (4) floating abstinence. Statistical significance of these coefficients will be assessed using a p-value with a two-sided $\alpha=0.05$, and both the odds ratio and its 95% confidence interval (CI) will be reported. Motivation and confidence to quit are evaluated on a continuous scale (0-10), and linear regression models will be used for both, with group (e-cigarette vs. control) as the covariate (along with any other baseline differences as covariates). To fully capitalize on the longitudinal nature of our data, secondary analyses will include a) regression analyses where number of QA's are compared across groups using poisson or linear regression (depending on the distribution of QA's), b) latency to any quit attempt, and c) stability of e- and conventional cigarette use over time. We will also repeat above analyses: a) based on those who do vs. do not use e-cigarettes, and b) using quit attempts and abstinence of all tobacco products, including e-cigarettes.

Ancillary Analyses:

Moderator analyses We can examine if uptake and/or consequences are moderated by motivation to quit, dependence, concerns of health, and/or any potential changes in e-cigarette product. Mediation of "intervention" effects: For each potential mediator (e.g., changes in harm perception/likeability of e-cigarettes), we will fit logistic models to assess each individually for each outcome. Latent class analyses: Patterns of use may be explored using latent class or other latent variable models to investigate if subjects separate into "classes" of use, which may be defined via reduction in cigarette use, uptake patterns in e-cigarettes and/or patterns of quit attempts. Adverse Events (AE's): We will determine the incidence of AEs and the associated 95% CI. A chi-square test will determine if the rate of serious adverse events (i.e., requiring treatment or life threatening) is greater than 5%. Other: 1) We will examine the longest duration of non-smoking between groups via a two-sample t-test. 2) If sufficient data are available, we will also conduct statewide comparisons on outcomes of interest to determine the influence of policy variables like a) level of excise tax, or b) % of state that is smokefree. 3) Urine samples will be frozen, with options for future secondary data analyses of both anabasine/anatabine, two tobacco specific biomarkers, but currently very costly to analyze. 4) Our local lab is developing an assay for 3'OH, which when compared to cotinine, provides an index of nicotine metabolite ratio (138, 139) which could be used as a predictor of e-cigarette uptake, something never before assessed. We are unsure when this assay will be ready, and consider this only ancillary.

Conclusion

We believe this will be the best, **most rigorous test to date of the naturalistic population impact of e-cigarettes**. Methods are strengthened by 1) large sample size (the largest e-cigarette RCT), 2) nationwide

recruitment, with 3) locally recruited subset to assess biomarkers, and 4) multiple measures of outcome. The strong investigative team, coupled with our success in prior studies using similar methodology, collectively enhances the probability of success in achieving grant aims. The NIH and FDA have each articulated a clear

Abbreviated Timeline (Full Timeline within Human Subjects Protections)					
	Year 1	Year 2	Year 3	Year 4	Year 5
Study Prep. & Refine Protocol	1-6 mnths				
Cumulative N to start	100	285	470	570	609
Data Analysis					57-60 mnths
Manuscript Preparation					57-60 mnths

agenda to understand how smokers use e-cigarettes and what impact such use may have on behavior. The proposed study offers the most methodologically rigorous test of these questions.

Human Subjects Research

1. Risks to Human Subjects

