We will advertise nationally but in select number of cities, with separate localized recruitment of a subset of smokers. We will choose cities on the basis of exceeding national rates for minority and/or Hispanic populations; see Table 3 for *potential* cities, which have the added benefit to allow for geographic diversity. Advertisements will be spread across various media outlets (newspapers, radio, Facebook, craigslist). We will now also utilize a respondent-driven (i.e., RDS, referral) sampling program. The RDS sampling methodology is based on recruiting the eligible friends and acquaintances of each participant so that the sample “snowballs”. Participants will be told that they can tell friends or acquaintances that they think would be interested in the study about the study. Participants will be compensated \$30 for every person who enrolls (completes week 0 phone call) into the study. Individuals referred to the study may not reside in the same household as the study participant while the study participant is enrolled. All comers, both motivated to quit and not, will be eligible to participate. Eligibility criteria include: a) age 21+, b) current smoker of ≥ 5 cigarettes per day for ≥ 1 year, c) no recent history of cardiovascular distress (arrhythmia, heart attack in past 3 months; uncontrolled hypertension) or renal disease (e.g., dialysis) that would interfere with urinary biomarker assessment, d) neither pregnant nor breastfeeding, e) at least some concern for health effects of smoking ($>\text{none}$ at all on a Likert scale), f) no current use of cessation medication, and g) have not purchased in the past 6 months or ever regularly used (daily or weekly) a tank system, mechanical mod, or advanced personal vaporizer e-cigarettes (though previous use of cig-a-like devices will be allowed), h) no regular use (daily or weekly) of any e-cigarette (including cig-a-like devices) in the last 6 months, i) and no current use of other tobacco products, j) mobile device with capacity to receive SMS text and internet access (for purposes of diary completion and remote carbon monoxide breathalyzer using the mobile device; see below) k) no other household members are enrolled in the study, and l) no history of seizure disorder. We restrict the sample to smokers with at least some concern

Table 3: Potential Recruiting Cities (US Census Data)

	Population	% Minority ^a	% Hispanic
Aurora CO	339,030	27.1%	28.7%
Baton Rouge LA	230,058	29.3%	3.3%

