Finally, though we cannot fully ensure that this will be a representative sample, we make efforts toward that goal. One strategy is to pick cities with large, diverse populations, noted above in Table 3. But within a city, we are unsure how fast or slow recruitment might take, and we run the possibility that several hundred participants could come from one locale. We wish to avoid that and will impose an upper limit of 80 participants per city. As we approach this upper limit, we can limit further enrollment by either removing the ad or temporarily removing the screening link. We had to do this in one prior national survey when 300+ survey respondents joined over a 3-day weekend. Given the demands of phone calls and mailings on our end, we may have to take more explicit measures to titrate our flow if this should happen again. As a last resort, and if more than 80 participants enroll from one city, we may need to turn eligible people away, and will send them a letter to such effect ("thank you for your interest but our study has reached full capacity in your geographic area") and will include cessation referral information specific to that area.

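### Friend-referral recruitment may correlate uptake within referral chains, yet the Aim 1 precision figure assumes independent participants and the planned intervals make no provision for the links

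*Combined protocol and SAP*

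**What the plan says.** All references are to the combined protocol and SAP.

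- **Recruitment** (Participant Eligibility, Consenting Process, Recruitment Feasibility, and Retention). Beside advertising in newspapers, radio, Facebook and craigslist, the study adds a second source: "We will now also utilize a respondent-driven (i.e., RDS, referral) sampling program". The mechanism is stated: "The RDS sampling methodology is based on recruiting the eligible friends and acquaintances of each participant". The referrer is paid $30 "for every person who enrolls (completes week 0 phone call) into the study". That section gives no maximum number of referrals per person.
- **Limits on concentration** (same section). One eligibility criterion is that "no other household members are enrolled in the study", and the investigators "will impose an upper limit of 80 participants per city".
- **Randomization.** Individuals are randomized 2:1, stratified by desire to quit and by local recruitment. Referral source is not a stratum.
- **Primary outcome** (Data and Safety Monitoring Plan, section 2). This is uptake of e-cigarettes. The sample size section gives tighter intervals for this single-arm outcome as the reason for 2:1 allocation.
- **Precision** (Precision of Proportional estimates within Aim 1). With 440 e-cigarette participants, "a two-sided 95.0% confidence interval will have a maximum half-width of 0.047". Of the rounded width the plan says: "A confidence interval as wide as +/- 5% is a relatively small width and one we are willing to accept".
- **Analysis** (Statistical Considerations – Data Analyses, Hyp 1a; repeated in substance in section 9 of the monitoring plan): "We will estimate each of these parameters, and the 95% confidence interval for each proportion". No variance method is named, and referral links appear in no analysis.

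**The concern.** Trying, using, buying and recommending a product are social behaviours, and the plan itself counts recommending to others as a form of uptake. Friends who join through one another may resemble or influence each other on these outcomes. If they do, 440 participants carry less information about an uptake proportion than 440 unrelated people. A standard binomial interval would then claim more precision than it has and would cover the true rate less than 95% of the time.

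This matters because precision of these single-arm proportions is a stated aim of the design. It does not threaten the between-arm comparisons in the same way, since friends are randomized individually.

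**Working it through.** **1. Reproduce the plan's figure.** The half-width for independent observations is 1.96 × sqrt(p(1 − p)/n), with n = 440.

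- p = 0.50: 1.96 × sqrt(0.25/440) = 0.0467, giving 0.453 to 0.547.
- p = 0.90: 1.96 × sqrt(0.09/440) = 0.0280, giving 0.872 to 0.928.

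Both match the plan's two worked intervals, so its precision statement uses a design effect of 1.

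**2. Allow for referral clusters.** Let f be the share of participants in referral clusters, m the cluster size and ρ the correlation between two members. Under 2:1 individual randomization, a cluster-mate of an e-cigarette participant is also in that arm with probability about 2/3. Hence

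DEFF = 1 + f × (2/3) × (m − 1) × ρ, and half-width = 0.0467 × sqrt(DEFF) at p = 0.50.

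The coverage of the nominal 95% interval is 2Φ(1.96/sqrt(DEFF)) − 1.

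**3. Put in assumed values.** The documents give none of f, m or ρ.

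| f | m | ρ | DEFF | Half-width, p = 0.50 | Half-width, p = 0.45 | Coverage |
|---|---|---|---|---|---|---|
| 0.10 | 3 | 0.10 | 1.013 | 0.0470 | 0.0468 | 94.8% |
| 0.25 | 3 | 0.10 | 1.033 | 0.0475 | 0.0473 | 94.6% |
| 0.50 | 3 | 0.10 | 1.067 | 0.0483 | 0.0480 | 94.2% |
| 0.50 | 3 | 0.20 | 1.133 | 0.0497 | 0.0495 | 93.4% |
| 0.50 | 5 | 0.20 | 1.267 | 0.0526 | 0.0523 | 91.8% |

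These rows illustrate the range; they do not bound it.

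**4. Design effect at which the half-width reaches 0.05.** This is (0.05/half-width)² at n = 440, for each hypothesized rate and for the 50% worst case.

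| Rate | Independent half-width | DEFF needed |
|---|---|---|
| 50% (worst case) | 0.0467 | 1.145 |
| 45% (regular use) | 0.0465 | 1.157 |
| 25% | 0.0405 | 1.53 |
| 20% | 0.0374 | 1.79 |
| 10% or 90% | 0.0280 | 3.18 |

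At 50%, this means an effective sample below about 384 (440/1.145), or f(m − 1)ρ above 0.145/(2/3) ≈ 0.22.

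**5. Sensitivity to the correlation pattern.** The last row of step 3 gives every pair in a chain of five the same ρ = 0.20. Suppose instead that 0.20 holds only between referrer and referred, and that it multiplies along links.

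- Line of five: average pairwise correlation (4 × 0.2 + 3 × 0.04 + 2 × 0.008 + 0.0016)/10 = 0.094. DEFF = 1 + 0.5 × (2/3) × 4 × 0.094 = 1.125, half-width 0.0495.
- One person referring four: (4 × 0.2 + 6 × 0.04)/10 = 0.104. DEFF = 1.139, half-width 0.0499.

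Both stay just inside 0.05.

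**6. Between-arm comparisons.** In a difference of proportions, a participant has weight 1/440 with probability 2/3 and −1/220 with probability 1/3. The mean weight is (2/3)/440 − (1/3)/220 = 0. If correlation is similar within and across arms, same-arm and opposite-arm pairs therefore cancel on average.

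**The case against.** The strongest reply is that every input driving the size is assumed. Advertising remains a recruitment source, so referrals may be few and chains short. The first two rows of the step 3 table then apply, and the effect is negligible. This stands, and it is why the point is conditional. Independence is also an assumption, however, and the plan neither states nor defends it for a sample meant partly to grow through friends.

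Several narrower replies also stand:

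- The household rule, individual randomization and the exclusion of recent regular e-cigarette users reduce within-arm clustering. They do not remove it. The city cap does not limit a chain of friends living in separate homes.
- A cap on referrals could appear in the consent pages, which are not in the available copy.
- The ±5% is a width that the plan is content with. It is not a decision rule, and no test or stopping boundary depends on it.
- Selection through volunteering and snowball recruitment may matter more for a single-arm rate than the interval width does. The protocol acknowledges selection by e-cigarette interest.

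A reader might go further and infer that the plan prescribes a binomial variance for Hyp 1a, that referral certainly makes participants correlated, or that the uptake intervals generally exceed ±5%. The documents support none of these. The Hyp 1a text names no variance method, no correlation is reported anywhere, and most hypothesized rates need a design effect of 1.5 or more to pass 5%. A scenario with the whole sample in referral chains does not fit the mixed recruitment described.

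**Conclusion.** The point holds in conditional form. The half-width of 0.047 assumes 440 independent participants, the recruitment method gives reason to doubt that, and the analysis text does not provide for it. If uptake is positively correlated within chains, standard binomial intervals will be too narrow for all the Aim 1 uptake proportions.

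Under the assumed values with part of the sample referred, the effect runs from trivial to moderate: at worst, in that range, the half-width at 50% is 0.053 and coverage about 92%. Passing ±5% is a realistic prospect mainly for outcomes near 50%. Among the hypothesized rates that means 45% regular use, and even there it depends on how correlation behaves along a chain. The between-arm tests, including 6-month abstinence on which the trial is powered, are little affected. This is an inexpensive improvement to the reporting of the primary outcome. It does not call for a larger sample.

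**What to change.** 1. Keep the referrer's study ID for each referred participant in the analysis dataset. Some such link is presumably needed to make the $30 payment, and it is easier to retain now than to reconstruct later.
2. In Hyp 1a, in both places where it appears, specify that the 95% intervals use variance clustered on referral chain, or an interval based on the effective sample size. Participants who were not referred and referred no one are clusters of one. If clustering proves negligible, the results will be close to the binomial intervals.
3. In the Aim 1 precision paragraph, state that 0.047 assumes independent participants. Give the half-width at 50% for design effects of 1.1 to 1.5: 0.0467 × sqrt(1.1) = 0.049 to 0.0467 × sqrt(1.5) = 0.057.

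The cost is one retained variable, a short addition to the analysis text and slightly wider reported intervals. Enrollment, randomization and study procedures do not change. The fix does not address selection bias from volunteer or snowball recruitment, nor any similarity among unreferred participants from the same city.

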1.3.2 Concurrent use of e-cigarettes and smoking

If smokers engage in dual use, the major concern will be intake of nicotine, and too much of it. Symptoms of nicotine intoxication include nausea, dizziness, headache, and stomachache (140). In our two prior studies wherein participants who used nicotine gum/lozenge and smoked concurrently, there was no evidence of nicotine intoxication (75, 76), nor have we seen serious adverse events in our current e-cigarette studies. We recently completed a literature review (141) that showed combined NRT, as well as concurrent use of NRT and smoking, were both safe.

[name] (co-I) recently completed a short term observational study, in which 20 smokers were provided e-cigarettes for ad libitum use over a 2 week period; i.e., a study very similar to current proposal. Data below demonstrate that changes (increases) in e-cigarette use increased in direct proportion with changes (decreases) in cigarette smoked (1st and 2nd panel), resulting in no net change in nicotine (3rd panel). Thus, smokers who engage in dual use are likely to NOT increase total nicotine intake, a finding replicated elsewhere (17). These findings are very much consistent with our own prior work on smokeless tobacco, wherein we provided smokers snus to use ad libitum over two weeks, finding no net increase in nicotine intake.

1.3.3 Undermining Cessation Another potential risk is that the sampling intervention will decrease rather than increase future cessation. We are aware of one recent longitudinal study (61) that showed numerically lower but still statistically similar rates of non-smoking among e-cigarette users vs. non-users, but this study did not assess for timing of e-cigarette use. This is the only study to show this that we are aware of. However, most of the available data available suggest that e-cigarettes either do not affect cessation or increase it (32, 44-46, 56, 66, 67).

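### The claimed ability to detect a fall in quitting from 8% to 4% carries only about 53–57% power; the odds ratio and interval cited for it describe a just-significant observed result

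*Combined protocol and SAP*

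**What the plan says.** Under Statistical Considerations – Sample Size & Power, the trial is sized on 7-day point prevalence abstinence at 6 months: "We power on a RR of 2.0: 8% vs. 16" percent. Allocation is 2:1, the target is 80% power, and the test is a two-sided 0.05 chi-square. The result is 600 participants, inflated to 660 (440 e-cigarette, 220 control) for attrition. The section says of group differences in quitting that "it would be entirely shortsighted if we lacked sensitivity (i.e., power) to demonstrate them".

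After Table 4 the plan states: "With this sample, we have 80% power to detect differences of 10% vs. 18.5" percent. The next sentence turns to the harmful direction and says "we are able to detect a decrement of 4% (8% vs. 4%; OR = .48; 95% CI: 0.23 - 0.98"). It gives no power for this. Table 4 covers only increases in quitting.

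For the analysis of Hyp 3, logistic regression on group is planned, and "both the odds ratio and its 95% confidence interval (CI) will be reported". Section 1.3.3 of Human Subjects Research names the hazard: "Another potential risk is that the sampling intervention will decrease rather than increase future cessation". Undermining of cessation is also addressed in section 2.2.3 and in the Data and Safety Monitoring Plan, sections 13 and 21.

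**The concern.** A confidence interval around a hypothetical observed difference answers one question: would that result be significant if it were seen? Power answers another: how often would a significant result occur if the true rates were these? When the assumed effect lies close to the significance boundary, as here, power is close to one half, because sampling error puts the observed difference below the boundary nearly as often as above it.

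The sentence sits in a power section, directly after an 80% power statement, and the same section treats sensitivity and power as one thing. The natural reading is that a halving of the quit rate would be found with about the usual probability. If it would not, a non-significant comparison of abstinence says little against a halving, and a reader relying on this sentence could conclude the opposite.

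**Working it through.** **Inputs** (Sample Size & Power): control rate 8%; e-cigarette rate 16% (benefit) or 4% (harm); two-sided 0.05; 2:1 allocation; 400/200 evaluable or 440/220 enrolled.

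**Formula.** With control rate p_c, e-cigarette rate p_e, arm sizes n_c and n_e, and pooled rate p̄:

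- s0 = √[p̄(1−p̄)(1/n_c + 1/n_e)]
- s1 = √[p_c(1−p_c)/n_c + p_e(1−p_e)/n_e]
- power ≈ Φ[(|p_c − p_e| − 1.96·s0)/s1]

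**1. The plan's own sizing.** For 8% vs 16% at 400/200: p̄ = 0.1333, s0 = 0.02944, s1 = 0.02653; (0.08 − 0.05770)/0.02653 = 0.840, so power is 80.0%. Solving for 80% power gives N = 603 against the stated 600. Without continuity correction the formula also matches the other cells checked in the 5%, 8% and 10% control rows of Table 4. For 10% vs 18.5% it gives 79% at 400/200 and 83% at 440/220.

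**2. The plan's odds ratio and interval.** Take 16/400 vs 16/200:

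- OR = (16/384)/(16/184) = 0.479
- SE of log OR = √(1/16 + 1/384 + 1/16 + 1/184) = 0.365
- 95% CI = exp(−0.736 ± 1.96 × 0.365) = 0.234 to 0.979
- chi-square p = 0.040; Wald p = 0.044

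This is the stated OR .48 (0.23–0.98). The same rates at 440/220 give 0.242 to 0.947, so the sentence was computed on 600. With one more quitter in the e-cigarette arm (17/400 vs 16/200), p = 0.058 and the CI is 0.25 to 1.03.

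**3. Power for a true 8% vs 4%.**

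- 400/200: p̄ = 0.0533, s0 = 0.01946, s1 = 0.02154; (0.04 − 0.03814)/0.02154 = 0.086, so power is 53%.
- 440/220: s0 = 0.01855, s1 = 0.02054; (0.04 − 0.03636)/0.02054 = 0.177, so power is 57%.

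| Method | 400/200 | 440/220 |
|---|---|---|
| Pooled normal approximation | 53% | 57% |
| Exact, uncorrected chi-square | 54% | 58% |
| Exact, Wald test on log OR | 52% | 55% |
| Exact, continuity-corrected chi-square | 46% | 50% |
| One-sided 0.05, normal approximation (not the plan's test) | 64% | 68% |

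No variant reaches 80%. The total N for 80% power is about 1188.

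**4. What 80% power does cover.** Against a control rate of 8%, the e-cigarette rate must fall to about 2.7% (600) or 2.9% (660), a decrement of about 5.3 or 5.1 points.

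**5. Other control rates.** The plan reports 4–13% in its earlier studies. Power for a halving:

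| Control rate | 4% | 5% | 8% | 10% | 13% |
|---|---|---|---|---|---|
| 400/200 | 32% | 38% | 53% | 63% | 74% |
| 440/220 | 34% | 40% | 57% | 66% | 78% |

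**6. The plan's own standard.** The section says that detecting 5% vs 10% is not feasible. Table 4 gives N = 1015 for it, and the formula gives 56% power at 400/200. The 8% vs 4% comparison, said to be detectable, has 53% at the same size.

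**7. What the interval can do.** If both true rates are 8%, exact enumeration gives a 67% (600) or 72% (660) chance that the 95% CI for the risk ratio lies wholly above 0.5. The interval can speak to a halving where the p-value cannot.

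**The case against.** No number in the sentence is wrong, and it states no power. A statistical reader may see that an interval just excluding 1 describes an observed difference. The plan nowhere says that a non-significant result will be read as absence of harm; it commits to reporting the odds ratio and interval, and it cautions against over-reading its own pilot's cessation results because the intervals were wide. Undermining is also examined through quit attempts, floating abstinence and the monitoring board. The primary outcome is uptake, and Hyp 3 predicts increases. Finally, with missing outcomes set to baseline the default denominator is 660, where one further e-cigarette quitter (19/440 vs 18/220) would still be significant (upper limit 0.986).

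Much of this is fair. The figures are correct as a description of an observed result, and the consequence is limited to interpretation. But the section's own usage, in which sensitivity means power and 5% vs 10% is out of reach, gives the sentence a meaning that the design does not support. The other checks on undermining give no power for a fall in abstinence. The larger denominator raises power only to 57%, and if 8% and 4% are rates among respondents, counting missing participants as smokers lowers both and 57% becomes an upper figure.

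**Conclusion.** The concern holds. The claim that the trial can detect a fall from 8% to 4% rests on an odds ratio and interval that show only that such an observed result would be just significant. If those were the true rates, the trial would miss the fall in 43% to 47% of repetitions. The power figures assume the plan's 8% control rate, 2:1 allocation and a two-sided 0.05 test. They take no account of the planned O'Brien–Fleming interim look; if the final level were 0.048, for illustration, they would be 52.8% and 56.4%. Over control rates of 4% to 13%, a halving never reaches 80% power at either sample size. The sizing on 8% vs 16% is sound and is not in question.

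**What to change.** Replace the sentence with wording such as: *For a decrease in quitting, power is about 53% for 8% vs 4% with 600 evaluable participants (57% with 660); 80% power is reached only for a fall from 8% to about 2.7% (2.9% with 660). An observed 8% vs 4% would be just significant (OR 0.48, 95% CI 0.23–0.98 at 400/200).*

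Add one clause to the Hyp 3 analysis, both under Data Analyses and in section 9 of the Data and Safety Monitoring Plan: any statement about undermining of cessation will rest on the odds ratio and its 95% confidence interval, not on a p-value above 0.05.

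The cost is one restated sentence and one clause of interpretation. The stated sensitivity to harm becomes less favourable. No new margin, analysis or enrolment is needed.
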